### **6.7.3 Management of Hemoglobin Decreases**

Reductions in hemoglobin are a well characterized side effect of ribavirin exposure. If a subject experiences a hemoglobin decrease meeting one of the criteria outlined in [Table 13](#), a confirmatory test should be performed. If the hemoglobin decrease is confirmed, the management guidelines in [Table 13](#) should be followed. Management will be different for subjects without a history of known cardiac disease and subjects with known cardiac disease.

Use of hematologic growth factors (such as erythropoietin or filgrastim) or blood transfusions are permitted at the discretion of the Investigator. Management of hematologic growth factor therapy is the responsibility of the Investigator, and growth factors will not be provided by AbbVie.

Alternate management of hemoglobin decreases outside of these criteria requires approval of the AbbVie Study Designated Physician.

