**Table 13. Ribavirin Dose Modification Guidelines in Management of Hemoglobin Decreases**

Hemoglobin Value	Intervention
All subjects	
< 10 g/L and $\geq$ 8.5 g/dL for subjects without cardiac disease	Reduce RBV dose*. Study drugs may be continued. If hemoglobin increases to $\geq$ 10 g/dL for subjects without cardiac disease or to 12g/dL for subjects with cardiac disease. RBV dose may be increased gradually in 200 mg increments towards original dose.
< 12 g/L and $\geq$ 8.5 g/dL for subjects with cardiac disease	
< 8.5 g/dL	Interrupt ribavirin. Manage the subject as medically appropriate. Investigator should evaluate if RBV discontinuation is warranted. If subsequent hemoglobin results are improved to $\geq$ 10 g/dL for subjects without cardiac disease or 12 g/dL for subjects with cardiac disease RBV, may be restarted.
Additional guidance for subjects with history of stable cardiac disease	
Hemoglobin decrease of $\geq$ 2 g/dL during any 4-week treatment period	Reduce RBV dose*. If a subsequent hemoglobin result is greater than the level that triggered the dose reduction, RBV dose may be increased gradually in 200 mg increments
< 12 g/dL after a 4-week RBV dose reduction	Interrupt ribavirin. Manage the subject as medically appropriate. Investigator should evaluate if RBV discontinuation is warranted. If subsequent hemoglobin results are improved to $\geq$ 12g/dL, RBV may be restarted.

\* 1st dose reduction of ribavirin is to 600 mg/day. If needed, 2nd dose reduction of ribavirin is by an additional 200 mg/day. Subjects whose dose of ribavirin is reduced to 600 mg daily receive one 200 mg tablet in the morning and two 200 mg tablets in the evening.

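### Table 13 gives cardiac subjects two conflicting conditions for raising ribavirin again, and one allows an increase while hemoglobin is still in the reduction band

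*Protocol*

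**What the plan says.** Protocol Section 6.7.3 makes Table 13 the operating rule for confirmed hemoglobin decreases. It begins "If the hemoglobin decrease is confirmed, the management guidelines in" and goes on to say that the table should be followed. It adds: "Alternate management of hemoglobin decreases outside of these criteria requires approval of the AbbVie Study Designated Physician".

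Four parts of Table 13 bear on a subject with cardiac disease:

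- **All-subjects block, reduction row.** Ribavirin is reduced when hemoglobin is below 12 and at least 8.5 g/dL. (The upper limit is printed in g/L, which I read as g/dL.) The condition for going back up is recovery "or to 12g/dL for subjects with cardiac disease. RBV dose may be increased gradually in 200 mg increments towards original dose".
- **All-subjects block, below 8.5 g/dL.** Ribavirin is interrupted. For cardiac subjects, restart needs 12 g/dL.
- **Fall-based row**, in the block headed "Additional guidance for subjects with history of stable cardiac disease". Ribavirin is reduced after a drop of at least 2 g/dL "during any 4-week treatment period". The condition for going back up is: "If a subsequent hemoglobin result is greater than the level that triggered the dose reduction, RBV dose may be increased gradually", in 200 mg steps.
- **Four-week row**, in the same block. The criterion is "< 12 g/dL after a 4-week RBV dose reduction". Ribavirin is interrupted, and restart needs at least 12 g/dL.

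The table's footnote sets the first reduction at 600 mg/day. Neither the table nor Section 6.7.3 says which condition governs when both reduction rows apply to the same subject.

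**The concern.** A fall of 2 g/dL or more that ends below 12 g/dL triggers both reduction rows. From then on the subject has two conditions for re-escalation: an absolute one (12 g/dL) and a relative one (anything above the subject's own triggering value). The relative condition has no floor, so it can allow an increase at a hemoglobin that another row of the same table treats as a reason to reduce.

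The 12 g/dL level is the table's own standard for cardiac subjects. It is used for re-escalation, for restart after a value below 8.5 g/dL, and for both interruption and restart in the four-week row. Only the fall-based row lacks it.

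At stake are the safety of subjects with cardiac disease on a drug known to lower hemoglobin, and uniform dosing across about 18 sites. An investigator who raises the dose early can point to a printed row, so the increase might not be seen as management outside the criteria and might not prompt the request for sponsor approval.

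**Working it through.** There is no sample size, power or error-rate figure to reproduce. The check applies the rules to the same subject side by side.

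**Rules, from Table 13.** Let S be the hemoglobin at the start of the 4-week period, T the triggering value and F a later value, all in g/dL.

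- All-subjects reduction row applies if 8.5 ≤ T < 12. Increase permitted if F ≥ 12.
- Fall-based row applies if S − T ≥ 2. Increase permitted if F > T.
- Both apply if S − T ≥ 2 and 8.5 ≤ T < 12. The conditions then disagree when T < F < 12, an interval of width 12 − T.

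**Worked case: 13.5 to 11.4, then 11.6**

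| Check | Result |
|---|---|
| Fall: 13.5 − 11.4 = 2.1 ≥ 2 | fall-based row applies |
| 8.5 ≤ 11.4 < 12 | all-subjects reduction row applies |
| 11.6 > 11.4 | fall-based row permits an increase, 600 to 800 mg/day |
| 11.6 < 12 | all-subjects row does not permit it |
| 8.5 ≤ 11.6 < 12 | still in the reduction band |
| Width of disagreement: 12 − 11.4 | 0.6 g/dL |

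**Width for a fall of exactly 2.0 g/dL** (the starting values are illustrative assumptions)

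| S | T = S − 2.0 | 12 − T |
|---|---|---|
| 12.5 | 10.5 | 1.5 |
| 13.0 | 11.0 | 1.0 |
| 13.5 | 11.5 | 0.5 |
| 14.0 | 12.0 | 0 |

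**Direction.** All combinations were enumerated on a 0.1 g/dL grid, with S from 10.5 to 17.0, T from 8.5 to 11.9 with a fall of at least 2, and F from 8.5 to 17.0. In 32,725 of 147,490 combinations the fall-based row permits an increase and the 12 g/dL condition does not. In none is it the other way round. These are grid points, not subjects, and say nothing about frequency. They show that the disagreement always runs in the less cautious direction.

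**Where there is no conflict.** For 14.5 to 12.5, then 12.8: the fall is 2.0, 12.8 > 12.5 and 12.8 ≥ 12, so both conditions are met. If the value falls below 8.5 g/dL, the interruption row applies instead.

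**Timing.** Table 5 schedules hematology at Weeks 1, 2, 4, 6, 8, 10 and 12. A reduction at Week 2, 4, 6 or 8 has a scheduled result two weeks later, before the four-week row can act. With a reduction at Week 4, a value of 11.6 at Week 6 permits an increase under the fall-based row. If the dose is not raised, the same 11.6 at Week 8 calls for interruption.

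**The case against.** The strongest reply is that the rows are cumulative. The lower block is headed as additional guidance, so it adds to the all-subjects block and does not replace it. A cardiac subject at 11.6 g/dL is still in the all-subjects reduction band, so raising the dose departs from a row that still applies and arguably needs sponsor approval. On this reading the relative condition has a sensible job. It covers falls that end at or above 12 g/dL, where a fixed 12 g/dL target would be met at once.

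That reading is plausible and may be the intended one, but the table does not state it. The fall-based row is not limited to triggers at or above 12 g/dL, and its permission is printed without qualification. For this reason I say only that an increase at 11.6 g/dL might not prompt the approval step.

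A second reply is that the triggering level could mean the 12 g/dL threshold. This would remove the conflict, but the row's own trigger is a relative fall with no fixed threshold, so the subject's own value is the natural reading.

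Third, the four-week contrast is partly by design, since failing to recover after four weeks is meant to lead to stronger action. That is fair. The conflict does not rest on that contrast; it rests on the two re-escalation conditions.

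Fourth, the practical effect is limited. Both permissions are optional, and an investigator who waits for 12 g/dL complies with every row. Steps are 200 mg, and hematology is frequent. Hemoglobin below the lower limit of normal at screening is excluded, and the 8.5 g/dL and four-week rows remain as backstops. All of this stands. It limits the harm but does not prevent the early increase.

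**Conclusion.** The concern holds. For a subject with stable cardiac disease whose fall of at least 2 g/dL ends between 8.5 and just under 12 g/dL, Table 13 prints two re-escalation conditions. They disagree for every later value above the trigger and below 12 g/dL. The gap is 12 minus the triggering value: 0.6 g/dL in the worked case, and 0 to 1.5 g/dL for the illustrative starting values. There is no conflict for triggers at or above 12 g/dL.

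This rests on reading the printed g/L as g/dL, on reading the triggering level as the subject's own value, and on the absence of any stated precedence between the rows.

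The protocol does not give the number of subjects with cardiac disease, so no expected count can be claimed. Hemoglobin falls are not rare on this regimen, however: Protocol Table 3 reports values below 10 g/dL in 7.2% of cirrhotic subjects on the 12-week arm. The SVR analyses and the yes/no subgroup for ribavirin dose modification are not affected. This is a safety-rule correction that should be made.

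**What to change.** Amend the fall-based row of Table 13 so that ribavirin may be raised in 200 mg steps only if a later hemoglobin both exceeds the value that triggered the reduction and is at least 12 g/dL. This brings the row into line with the other cardiac rows, makes the cumulative reading explicit, and changes nothing when the trigger is 12 g/dL or higher.

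The cost is one line in a protocol amendment, with no added visits or tests. The only downside is that some cardiac subjects may stay longer on reduced ribavirin.

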#### 6.7.4 Management of Transaminase Elevations

Transient asymptomatic Grades 3 – 4 ALT elevations have been observed in approximately 1% of subjects receiving ABT-450/r-containing regimens. If a subject experiences an increase in ALT to  $> 10 \times$  ULN, or to  $> 5 \times$  ULN which was increased from previous measurement, the subject should have a confirmatory ALT measurement performed in a timely fashion. If the ALT increase is confirmed, the management guidelines in [Table 14](#) should be followed. Subjects using an estrogen-containing product should discontinue use of that product. Alternate management of ALT increases is permitted with approval of the AbbVie Study Designated Physician.

**Table 14. Management of Confirmed ALT Elevations**

ALT $\geq 20 \times$ ULN	
 
• Permanently discontinue study drugs.
 
• Manage the subject as medically appropriate.
 

ALT $\geq 10 \times$ ULN or ALT $\geq 5 \times$ ULN and increased from previous measurement with symptoms and signs of hepatitis present	
 
• If using an estrogen-containing product: Discontinue estrogen-containing product and repeat ALT testing, preferably within 1 week.
 
• Repeat ALT, AST, total and fractionated bilirubin, alkaline phosphatase and INR, preferably within 1 week.
 
• Evaluate for alternative etiology of ALT elevation: update medical history and concomitant medications eCRF (if applicable), and obtain additional testing as appropriate.
 
• Manage the subject as medically appropriate.
 
• Permanently discontinue study drugs for any of the following: ALT level increases to <math>20 \times</math> ULN, increasing direct bilirubin, increasing INR, or new symptoms/signs of hepatitis.
 

ALT $\geq 5 \times$ ULN and increased from previous measurement but $< 10 \times$ ULN and without symptoms or signs of hepatitis	
 
• Continue study drugs.
 
• As soon as possible, measure ALT, AST, total and fractionated bilirubin, alkaline phosphatase and INR. Repeat liver chemistries as indicated until resolution. Evaluate for alternative etiology of ALT elevation: update medical history and concomitant medications eCRF (if applicable), and obtain additional testing as appropriate.
 
• Manage the subject as medically appropriate.
 
• Permanently discontinue study drugs for any of the following: ALT level increases to <math>20 \times</math> ULN, increasing direct bilirubin, increasing INR, or symptoms/signs of hepatitis.
 

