**Table 2. Overview of Treatment-Emergent Adverse Events (AE)**

	Placebo-Controlled		Regimen-Controlled		Cirrhotics	
	12-Week 3-DAA + RBV	12-Week PBO	12-Week 3-DAA + RBV	12-Week 3-DAA	12-Week 3-DAA + RBV	24-Week 3-DAA + RBV
Events, %	N = 770	N = 255	N = 401	N = 509	N = 208	N = 172
Subjects $\geq$ 1 AE	89.0	76.9	82.8	75.0	91.8	90.7
Severe AE	3.5	0.4	1.0	1.2	6.7	7.6
Grade 3 or 4 AE	3.9	0.8	3.0	2.0	7.7	8.1
Serious AE	2.1	0.4	2.2	1.4	6.3	4.7
AE leading to discontinuation	0.8	0.4	0.5	0.4	1.9	2.3
Deaths	0.1 a	0	0	0	0.5 b	0

PBO = Placebo

a. Lung cancer.

b. Metformin toxicity, lactic acidosis, multi-organ system failure.

The most common adverse events regardless of causality are listed in [Table 3](#). Adverse events that occurred at a  $\geq 5\%$  incidence in the 3-DAA + RBV regimen versus the placebo were considered to be adverse drug reactions related to the study treatment. These include fatigue, nausea, pruritus, insomnia, asthenia, and anemia. These events were mostly attributable to ribavirin as the rates were lower in the RBV-free arm, and were similar to the placebo rates observed in the placebo-controlled cohorts. In general, rates of adverse events were similar in patients with cirrhosis versus patients without cirrhosis. Patients with cirrhosis had a higher frequency of bilirubin elevations.

**Table 3. Treatment-Emergent Adverse Events with  $\geq 10\%$  Frequency in at Least One Arm of the Analysis and Rates of Key Post-Baseline Lab Abnormalities**

	Placebo-Controlled		Regimen-Controlled		Cirrhotics	
	12-Week 3-DAA + RBV	12-Week PBO	12-Week 3-DAA + RBV	12-Week 3-DAA	12-Week 3-DAA + RBV	24-Week 3-DAA + RBV
Treatment-emergent Adverse Events, %	N = 770	N = 255	N = 401	N = 509	N = 208	N = 172
Headache	34.3	29.8	24.4	25.1	27.9	30.8
Fatigue	34.2	26.3	29.9	26.5	32.7	46.5
Nausea	22.3	14.9	15.7	8.4	17.8	20.3
Pruritus	15.7	4.3	12.0	6.1	18.3	19.2
Insomnia	14.0	7.5	12.2	5.1	15.4	18.0
Diarrhea	13.5	9.0	8.7	11.4	14.4	16.9
Asthenia	13.5	6.7	9.0	3.9	13.9	12.8
Rash	10.0	5.9	6.2	3.7	11.1	14.5
Cough	8.7	5.1	6.7	4.7	11.5	11.0
Irritability	5.3	4.7	3.2	3.1	7.2	12.2
Anemia	5.3	0	7.5	0.2	7.7	10.5
Dyspnea	9.7	5.5	4.7	2.2	5.8	12.2
Laboratory Events, %	N = 765	N = 254	N = 401	N = 509	N = 208	N = 172
Hemoglobin						
< 10 g/dL (Gr 2)	5.5	0	6.2	0	7.2	11.0
< 8.0 g/dL (Gr 3)	0.1	0	0.5	0	1.4	0.6
ALT						
> 5 $\times$ ULN (Gr 3)	1.2	3.9	0.7	0.2	2.9	0
Bilirubin						
> 3 $\times$ ULN (Gr 3)	2.6	0	5.7	0.4	13.5	5.2

PBO = Placebo

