## **6.7.2                    Grades 3 or 4 Laboratory Abnormalities and Severe or Serious Adverse Events**

### **Grade 3 – 4 Laboratory Abnormalities**

With the exception of Grade 3 or higher abnormalities of total bilirubin, uric acid, phosphorus, total cholesterol, triglycerides, or glucose (in subjects with a history of diabetes), if a subject experiences a Grade 3 or greater abnormal laboratory parameter during the Treatment Period, the abnormal laboratory test should be repeated. If the Grade 3 or greater abnormality is confirmed, the investigator should assess whether the abnormality can be managed medically without interruption of study drug, or whether study drugs should be interrupted and the laboratory parameter followed until it improves. If study drugs are interrupted and restarted and the abnormality recurs, then study drugs should be permanently discontinued.

Decreases in serum hemoglobin or elevations of serum ALT should be managed according to the guidance in Section 6.7.4 and Section 6.7.5 below. Grade 3 or greater abnormalities of total bilirubin, uric acid, phosphorus, total cholesterol, triglycerides or glucose (in subjects with a history of diabetes) should be managed medically as appropriate and do not require confirmation or study drug interruption unless deemed necessary by the investigator.

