### **Severe Adverse Event or Serious Adverse Events**

If a subject experiences a severe adverse event or a serious adverse event that the investigator considers to be a reasonable possibility of relationship to study drug, investigator should assess whether the adverse event can be managed medically without interruption of study drug, or whether study drugs should be interrupted until it improves, or study drugs should be permanently discontinued. If study drugs are interrupted and restarted and the adverse event recurs, then study drugs should be permanently discontinued.

If a subject experiences a severe adverse event or serious adverse event that is considered unrelated (no reasonable possibility) to the study drugs, it is not necessary to interrupt study drugs unless an interruption is required because of the nature of the event (e.g., unable to take oral medications). If an interruption is required, it should not exceed 7 days.

The investigator should ensure that all serious adverse events are reported to AbbVie within 24 hours of awareness. Serious adverse event follow-up information, including associated dose interruptions (or discontinuations), must be reported to AbbVie within 24 hours of awareness by entering updated SAE information into the appropriate eCRFs.

Severe adverse events and any associated dose interruptions (or discontinuations) should be entered into the appropriate eCRFs.

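### Table 14, row 2: hepatitis symptoms already present at a confirmed, rising ALT of 5 to <10 x ULN are not clearly a stop trigger, although row 3 stops for them at the same ALT

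*Protocol*

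**What the plan says.** Section 6.7.4 sends every confirmed ALT increase to Table 14, which has three rows.

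- **Row 1:** ALT of 20 x ULN or more. Study drugs are stopped permanently.
- **Row 2:** ALT of 10 x ULN or more, or ALT of 5 x ULN or more and "increased from previous measurement with symptoms and signs of hepatitis present". The actions are stopping any estrogen product, repeat liver tests preferably within a week, a search for another cause, and medically appropriate management. Permanent discontinuation is required if ALT reaches 20 x ULN or for "increasing direct bilirubin, increasing INR, or new symptoms/signs of hepatitis".
- **Row 3:** a rising ALT from 5 to below 10 x "ULN and without symptoms or signs of hepatitis". Dosing continues with monitoring. Permanent discontinuation is required if ALT reaches 20 x ULN or for "increasing direct bilirubin, increasing INR, or symptoms/signs of hepatitis".

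Three other places bear on the question. Section 6.7.2, on laboratory abnormalities, says: "Decreases in serum hemoglobin or elevations of serum ALT should be managed according to the guidance in Section 6.7.4 and Section 6.7.5 below". For severe or serious events possibly related to drug, the same section says the "investigator should assess whether the adverse event can be managed medically without interruption of study drug", or whether to interrupt or stop. Section 6.7.4 adds: "Alternate management of ALT increases is permitted with approval of the AbbVie Study Designated Physician". Section 5.4.1 lets the investigator discontinue a subject at any time.

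**The concern.** Rows 2 and 3 meet at the same ALT band, 5 to <10 x ULN and rising. There the presence of hepatitis symptoms or signs should decide the action, but the two rows give it different weight. In row 3 their appearance alone forces a permanent stop. In row 2 they are the entry condition, and only 'new' ones force a stop. Whether the stop is mandatory then depends on whether symptoms began before or after the confirmatory test.

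The entry wording adds a second problem. Row 2 joins symptoms and signs with 'and'; row 3 excludes anyone with either.

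This is a hepatotoxicity stopping rule in a trial where every subject has cirrhosis. Different sites could handle the same clinical state differently.

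**Working it through.** **Tracing the rule.** Take a confirmed, rising ALT of 7 x ULN.

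| | Subject A | Subject B | Subject C |
|---|---|---|---|
| At confirmation | symptoms and signs | neither | symptoms, no signs |
| Row | 2 | 3 | neither, read literally |
| On entry | retest, work-up, management | continue dosing, monitor | not stated |
| Later course | unchanged, laboratory values stable | symptoms appear, same ALT | – |
| Mandatory stop | none on the plain reading | yes | not stated |

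Reassigning B to row 2 when symptoms appear changes nothing, because B's symptoms are new. So A and B reach the same state under different rules.

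**Looking for a stop elsewhere.** Section 6.7.2 refers ALT back to Section 6.7.4. Its rule for severe or serious events asks for an assessment. Section 5.4.1 is permissive. The alternate-management clause allows departures from the table but adds no stop. None closes the gap.

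**How often it could matter.** Inputs come from Table 3 (ALT >5 x ULN and its denominators).

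1. Cases rebuilt from the rounded percentages: 765 x 1.2% = 9; 401 x 0.7% = 3; 509 x 0.2% = 1; 208 x 2.9% = 6; 172 x 0 = 0. The total is 19 of 2,055, or 0.92%, which reproduces the roughly 1% given in the Introduction and Section 6.7.4.
2. The closest arm to this trial is the 12-week cirrhotic arm: 6/208 = 2.88%, Wilson 95% CI 1.33% to 6.15%, or about 3 (1 to 6) per 100. This is a ceiling. It includes subjects at 10 x ULN or more, where rows 2 and 3 do not overlap, and Table 14 also requires confirmation and, below 10 x ULN, a rise.
3. The Introduction describes the elevations as asymptomatic. Assume that covers all 19 cases. The one-sided 95% upper bound on the symptomatic share is 1 − 0.05^(1/19) = 0.146. With only the 6 cirrhotic cases it is 1 − 0.05^(1/6) = 0.393.
4. Affected per 100: 2.88 x 0.146 = 0.42, or 2.88 x 0.393 = 1.13. Using the upper ALT limit as well gives 6.15 x 0.146 = 0.90 and 6.15 x 0.393 = 2.42. These last two multiply two upper limits, so they have no stated coverage and serve only as outer values.

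**Symptoms with another cause.** In the same arm, fatigue (32.7%), pruritus (18.3%) and nausea (17.8%) were common. The Introduction says of a list that includes all three: "These events were mostly attributable to ribavirin as the rates were lower in the RBV-free arm". If each counted as a hepatitis symptom, and all were independent of each other and of ALT (assumptions), the share with at least one would be 1 − 0.673 x 0.817 x 0.822 = 0.548. That gives 2.88 x 0.548 = 1.58 per 100 (1.33 x 0.548 = 0.73 to 6.15 x 0.548 = 3.37). This overstates the number at issue, because it uses events from any time on treatment, not those present at the ALT rise.

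**The case against.** The strongest defence is that both rows follow one principle: stop on worsening after entry. Row 3 subjects enter without symptoms, so any symptom is a change. Some row 2 subjects enter with symptoms, so 'new' is needed to mark change. A sponsor may also want the search for another cause done before acting on symptoms seen at first confirmation. This explains how the wording could have arisen. It does not explain why symptoms alone suffice for a permanent stop in row 3 and not at entry to row 2.

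A second defence reads 'new' as new since baseline. Symptoms that began on treatment would then already require a stop and the conflict would disappear. Retesting would still have a purpose, since liver tests are followed after drug is stopped. The reading is possible, but the table does not state it. What remains is an ambiguity that a clarification should settle.

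A reader might infer that row 2 tells sites to keep dosing subjects with symptomatic hepatitis. It does not. The instruction to continue study drugs appears only in row 3, and row 2 leaves management to the investigator, who may interrupt or stop. Nor do the documents support calling the gap a cause of frequent harm, given that the earlier elevations were described as asymptomatic.

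**Conclusion.** The point stands as a low-priority clarification. Row 2 is ambiguous and, on its plain reading, inconsistent with row 3 at 5 to <10 x ULN. The 'and' against 'or' entry wording also leaves some subjects in neither row.

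The expected effect is about 0 to 1 subject per 100. That rests on the rate in the earlier 12-week cirrhotic arm carrying over to this Asian population, and on the description of earlier elevations as asymptomatic. The less favourable calculations above reach 2.4 only by stacking two upper limits. Prompt retesting, the laboratory stop triggers and investigator discretion limit the consequence further. Efficacy conclusions are unaffected.

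**What to change.** Change two phrases in Table 14, row 2, by amendment or clarification letter:

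1. Entry condition: *symptoms or signs of hepatitis present*.
2. End of the stop list: *or symptoms/signs of hepatitis that began or worsened after the first dose, whether present at confirmation or appearing later*.

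The second change fixes the meaning of 'new' and leaves out complaints that have been stable since before treatment. Asymptomatic subjects at 10 x ULN or more keep the existing retest and work-up pathway.

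Do not add an exception for symptoms the investigator attributes to ribavirin. Row 2 now stops unconditionally for new symptoms, including at 10 to <20 x ULN. Such an exception would make that a matter of judgement while row 3 stayed unconditional at lower ALT. Cases with another clear cause can use the alternate management with sponsor-physician approval already in Section 6.7.4.

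The cost is the rewording plus an occasional extra discontinuation, about 0 to 1 subject per 100, which could cost that subject SVR. If common ribavirin-type complaints were counted loosely as hepatitis symptoms, the number could approach the 1.6 per 100 above, so the approval route should be pointed out to sites.
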